9.8 Suspension of research

Due to the low risk of the intervention, it is unlikely that there will be a need to suspend the research. However, should the medical monitor identify any issues after reviewing the data, they can develop stopping rules for the trial, and the recommendations will be followed.

10.0 Risks

10.1 ECIG use:

- There may be some unknown risks related to the use of ECIGs though these risks are not considered to be greater than risks associated with conventional cigarette use.
- The most common side effects associated with using an ECIG are changes in taste, dehydration, mucus in throat/sinus, dry mouth, dry cough, throat irritation, mouth irritation, sore throat, mouth ulcers, dizziness, headache, and nausea.
- There are reports that some people who use e-cigarettes have experienced seizures, with most involving youth or young adult users. Participants with a history of seizures or take medications to prevent seizures will be excluded from the study.
- There have been some reports of serious lung illnesses among those who used e-cigarettes, and even some cases of death as a result (not all causes of death have been identified). The investigations being conducted by the Centers for Disease Control and Prevention (CDC) and the Food and Drug Administration (FDA) have found that the majority of people experiencing these

illnesses were using e-cigarette products that contained tetrahydrocannabinol (THC) and/or products that were bought off the street or from other illicit channels and so it is important that participants avoid such products. The e-cigarette products used in this study do not contain THC and were bought from manufacturers where quality testing and control is performed. Nonetheless, participants will be advised to call their doctor immediately if they experience cough, shortness of breath, chest pain, nausea, vomiting, diarrhea, or fever after using their e-cigarette. Participants will be told to only use the e-cigarette and liquid pods (cartridges) given to them by the researchers and to not tamper with their e-cigarette or use other liquids with the e-cigarette device.

- If stored improperly (in pocket or where the ECIG device can turn on accidentally), overheating of the device may occur, which presents a minor burn risk.
- Electronic cigarette liquid contains vegetable glycerin, propylene glycol and flavorings. Participants with known allergies to these substances will be excluded in the study. The most common reported allergic reaction to these substances is contact dermatitis.

10.2 Nicotine addiction: Participants may be given a study product that contains nicotine, which is an addictive substance. The amount of nicotine they receive from this product depends on what product they are given and how they use it.

10.3 Nicotine withdrawal symptoms: Smoking fewer conventional cigarettes may result in nicotine withdrawal symptoms (e.g. irritability, anxiety, restlessness, depressed mood, increased appetite, fatigue, difficulty concentrating). These symptoms will be monitored bi-weekly.

10.4 New development of pregnant or want to become pregnant: Nicotine, either from cigarettes or from the study product (ECIG), is known to be harmful to the developing human fetus. If you are pregnant or become pregnant, cigarettes and the study product (ECIG) may cause problems to your unborn baby. Women who are pregnant or are nursing a child may not participate in this research study. Females capable of becoming pregnant will be administered a pregnancy test prior to beginning the research. Participants must agree to take reasonable and necessary precautions against becoming pregnant during the period of the investigation. The investigator will discuss appropriate precautions with participants.

10.5 MRI (Magnetic resonance imaging) Risks: MRI does not involve radiation and there are no known long-term risks of MRI. Participants will be assessed for MRI safety at the screening visit and again at the scan visit before entering the scanner. We will be assessing for potential MRI hazards like metal fragments in the body or metal implanted devices that could shift during scanning. Participants will be instructed to remove all metal from their body and clothing before entering the scanning room. The major discomforts of fMRI scanning include lying still in a supine position for a sustained period of time and hearing loud tapping sound during image acquisition. Participants may be uncomfortable inside the MRI scanner, especially if they do not like to be in closed spaces ("claustrophobia"). In between scanning sequences, participants will be able to talk with the MRI staff through a speaker system. At any time, the participant can choose to stop the scan by squeezing a "panic" button.

10.6 Loss of confidentiality: There is a risk of loss of confidentiality if information is obtained by someone other than the investigators. Precautions will be taken to prevent this including direct coding of data in REDCap.

10.7 Randomization in clinical trials: Participants will be assigned to a research intervention by chance. The research intervention they receive may prove to have more side effects than the other research intervention(s).

10.8 Incidental Finding: None of the tests carried out in this study are intended to provide diagnoses for clinical purposes, but participants will be alerted to findings that should be discussed with a healthcare provider (such as high blood pressure or MRI findings). The MRI scans done during this study are NOT designed to detect or evaluate any medical condition. They are intended solely for research purposes. The investigators for this project are not trained to perform medical diagnosis,

and the scans to be performed in the study are not optimized to find abnormalities. On occasion, a member of the research team may notice a finding on a scan that seems abnormal. When a finding is noticed, one of the investigators may consult a physician specialist, such as a radiologist or neurologist, as to whether the finding merits further investigation. If the specialist recommends further follow-up, the investigator or another member of the research team will contact the participant within 48 hours (via a phone call) of the recommendation and suggest that the participant contact his or her private medical provider for follow-up. To facilitate follow-up care, the participant will be given a copy of the images via a letter if the subject would like one. Being told about a finding may cause the participant anxiety as well as suggest the need for additional tests and financial costs. Medical insurance may be affected whether or not the finding is ultimately proved to be of clinical significance. Costs for clinical follow-up will not be covered in the cost of research. Participants will be told that their decision as to whether to proceed with further examination or treatment is their own.

10.9 Questionnaires: It is possible that some of the questions in the questionnaires may make participants uncomfortable. They will be instructed that they are free to skip any questions that make them uncomfortable.

11 Potential Benefits to Subjects and Others

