3.2 Exclusion Criteria

1. Impaired smell function as measured via standardized screening assessment
2. Unstable or significant medical condition in the past 12 months (recent heart attack or some other heart conditions, stroke, severe angina including high blood pressure)
3. Severe immune system disorders (uncontrolled Human Immunodeficiency virus infection; unstable multiple sclerosis symptoms), respiratory diseases (exacerbations of asthma or chronic obstructive pulmonary disorder, require oxygen, require oral prednisone), kidney (dialysis) or liver diseases (cirrhosis), or any medical disorder/medication that may affect participant safety or biomarker data
4. Women who are pregnant (verified by urine pregnancy test at any visit), trying to become pregnant, or nursing
5. Medical conditions associated with cognitive impairment or neurological dysfunction
6. Severe claustrophobia
7. Current depressive or anxiety disorder
8. Uncontrolled mental illness or substance abuse or inpatient treatment for these conditions in the past 6 months
9. Use of illicit drugs or prescription drugs for non-medical use daily/almost daily or weekly in the past 3 months per National Institute on Drug Abuse (NIDA) Quick Screen, not including use of marijuana
10. Any known risk from exposure to high-field strength magnetic fields (e.g., cardiac pacemakers), any irremovable metallic foreign objects in their body (e.g., braces), or a questionable history of metallic fragments which are likely to create artifact on the MRI scans
11. Known allergy to propylene glycol or vegetable glycerin
12. Other member of household currently participating in the study
13. History of a seizure disorder or had a seizure in the past 12 months
14. Currently taking or who have taken medications prescribed to prevent seizures (such as Carbamazepine or Phenobarbital). Using seizure medications for off-label use (indications other than treatment for seizures) will not be included as an exclusion, these will be assessed on a case-by-case basis

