7.2.10 Flavor-Cue Reactivity Details

The olfactometer (ETT, inc: <http://www.emergingtechtrans.com>) will be used to deliver the e-liquid odors to the nose during a respiration-triggered event-related fMRI cue-reactivity task. The tobacco and strawberry vanilla e-liquid flavors, as well as two common control scents, Lavender and PEA (phenyl ethyl alcohol; that smells like rose), will be delivered in randomized order during 4-minute blocks over 8 runs. The flavors will be delivered for 4 seconds every 20-30 seconds depending on respiration rate. At the end of the task, participants will be delivered each odor again and asked to rate how much they like the flavor using a fiber-optic button box.

The lavender odor is an experimental control condition that encourages participants to maintain attention and task engagement during the MRI scan. It provides us with a quality control manipulation, whereby if we suspect from poor data quality that a participant was not paying attention in the scanner, we can confirm this if they were also not responding to the lavender scent as instructed.

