7.4 Test Article(s) (Study Drug(s) and/or Study Device(s))

7.4.1 Description

The ECIG used will be the EGO ECIG. Previous work has shown that the EGO ECIG was capable of delivering nicotine to its users.²⁶ This ECIG is made up of 2 parts, a battery and a cartomizer. The cartomizer contains the heating element and the liquid. The liquid used in the cartomizer will contain either 0 mg/ml or 18 mg/ml of nicotine and be either tobacco or strawberry vanilla

flavor. The nicotine concentration in the liquid and the flavor will be determined by random assignment. The cartomizers will be filled with liquid by the researchers and will be used once by the participant and returned to researchers.

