7.4.2 Treatment Regimen

Participants will be randomized to one of four conditions:

- Tobacco flavor ECIG (18 mg/ml nicotine concentration)
- Tobacco flavor ECIG (0mg/ml nicotine concentration)
- Strawberry Vanilla flavor ECIG (18 mg/ml nicotine concentration)
- Strawberry Vanilla flavor ECIG (0mg/ml nicotine concentration)

Participants will be instructed to use their ECIG for at least 50 puffs per day to replace conventional cigarette use.

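### Section 10.1 says known allergy to any listed e-liquid content, flavorings included, is excluded, but exclusion criterion 11 names only propylene glycol and vegetable glycerin

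*Combined protocol and SAP*

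**What the plan says.** Section 10.1 (Risks, ECIG use) describes the liquid: "Electronic cigarette liquid contains vegetable glycerin, propylene glycol and flavorings". The next sentence gives the mitigation: "Participants with known allergies to these substances will be excluded in the study". It then describes the usual reaction: "The most common reported allergic reaction to these substances is contact dermatitis".

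The operative list is section 3.2. Its only allergy entry is criterion 11: "Known allergy to propylene glycol or vegetable glycerin".

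Flavor is a randomized factor. Section 7.4.1 says: "The liquid used in the cartomizer will contain either 0 mg/ml or 18 mg/ml of nicotine and be either tobacco or strawberry vanilla". Section 7.4.2 says "Participants will be randomized to one of four conditions" and lists two flavors, each at two nicotine strengths. None of the four is unflavored. In section 7.2.10 the olfactometer "will be used to deliver the e-liquid odors to the nose during a respiration-triggered event-related fMRI cue-reactivity task", and both study flavors are presented to each scanned participant whatever the assigned arm.

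**The concern.** Exclusion before exposure is the protection that section 10.1 gives for the allergy risk. Staff screen from the list in section 3.2, so a protection described only in the risk section may not reach the person asking the questions. Here the missing item is present in every arm, and participants are told to take at least 50 puffs a day for four weeks.

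Earlier tolerance cannot be assumed either. Inclusion criterion 2 accepts cigarette smokers with no e-cigarette experience.

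At stake is a small, avoidable safety exposure, together with a protocol whose risk section and eligibility list do not match.

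**Working it through.** The check is a comparison of text. The plan gives no figure to reproduce.

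**Step 1. Compare the two statements.**

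| Content named in 10.1 | Exclusion stated in 10.1 | Named in criterion 11 |
|---|---|---|
| Vegetable glycerin | Yes | Yes |
| Propylene glycol | Yes | Yes |
| Flavorings | Yes | No |

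Three contents are listed and two are carried over: 3 − 2 = 1 omitted.

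**Step 2. Look for the omitted item elsewhere.** None of the 14 exclusion criteria in section 3.2 names flavoring allergy. The nearest is the closing clause of criterion 3, a general provision on disorders or drugs that bear on safety or on biomarker data. It mentions neither allergy nor flavorings. The withdrawal criteria in section 3.3.1 do not name it either.

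**Step 3. Count who is assigned the omitted content.** Section 7.4.2 gives 2 flavors × 2 nicotine strengths = 4 arms, and all 4 are flavored. Section 7.4.3 randomizes 56 people 1:1:1:1, so 56 / 4 = 14 per arm and 4 × 14 = 56 assigned to flavored liquid. This counts people assigned to the product. It does not count people at risk, because the documents give no rate of flavoring allergy.

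**Step 4. List the safeguards that could act before the product is used.**

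- Criterion 3, applied by judgment.
- Medical history at Visit 1 (Table 1), with doubtful histories referred to the medical monitor before randomization (section 9.1). Referral works from the eligibility criteria, so a list without flavorings gives staff no named trigger.
- The staff check for contraindications to the study products at each in-person visit (section 9.1). Visit 2 is in person and the device is handed over at its end (section 7.2.3), so the check falls before dispensing. Its contents are not listed.
- Phone Screener 2 and the Visit Screener (section 7.2.1). Neither form is in the documents, so whether they ask about flavoring allergy cannot be seen.

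**Step 5. List the safeguards that act afterwards.** Adverse events are monitored at every visit after Visit 1 (section 7.2.6). Section 3.3.1 allows withdrawal for events related to e-cigarette use, and removal at the investigator's discretion. These limit harm once a reaction has occurred, whereas section 10.1 promises exclusion beforehand.

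**The case against.** The strongest reply is that the protocol already excludes these people. Section 10.1 is part of the same protocol and says so, criterion 3 gives a basis for acting, and the contraindication check before dispensing is product-specific. If either screener asks about flavorings, nothing changes in practice. Much of this stands. A reader might infer that criterion 11 admits people with a flavoring allergy. The documents do not support that: criterion 11 fails to name them, which is different from letting them in. What remains is that every route to exclusion runs through judgment or through forms that cannot be seen. The other two contents were judged to need a named criterion.

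A second reply is that section 10.1 is a loose summary and that 'these substances' means only the two carrier liquids. This is weak. Flavorings are the last item named in the sentence immediately before, and the narrow reading has to skip them.

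A third is that the reaction is mild. Contact dermatitis is described as the most common reaction, which supports a low priority but does not make it the only one.

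A reader might also infer a parallel gap for seizures. Section 10.1 says "Participants with a history of seizures or take medications to prevent seizures will be excluded from the study", while criterion 13 limits a seizure outside a seizure disorder to the past 12 months. The documents do not support making this a defect. The sentence reads naturally as shorthand for criteria 13 and 14 together, and on medication it is narrower than criterion 14, which also covers past use. Nothing in the documents shows the 12-month limit to be inadequate, so widening it would be a preference.

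**Conclusion.** The mismatch holds for allergy. Criterion 11 names two of the three contents whose allergy section 10.1 says is excluded, and the third is in the liquid of all four arms. The text comparison is secure. It rests on reading 'these substances' as everything named in the preceding sentence.

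The practical consequence is less certain and probably small. It depends on the unseen screeners, on what the contraindication check covers, and on how many candidates know of such an allergy. The documents give no figure for the last, and none is assumed here.

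A reader might infer that late discovery threatens the 14 per arm, since section 3.3.2 describes replacement only for withdrawals before randomization. With no allergy rate in the documents, that inference has no support. The point concerns participant safety and internal consistency. It does not affect the endpoint, randomization, power or analysis, and it is worth correcting at low priority.

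**What to change.** Reword criterion 11 as: *Known allergy to propylene glycol, vegetable glycerin, or flavorings in the study e-liquids*. Confirm that Phone Screener 2 and the Visit Screener ask about it in the same terms, and add it explicitly to the contraindication check at Visit 2.

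Tying the wording to the study liquids keeps the question answerable: it concerns two flavors. The protocol does not give their constituents, and the liquids come from online vendors (section 7.4.6.1). The answer will therefore rest on what the participant knows unless the team obtains ingredient lists. The lavender and rose control scents are not e-liquid contents, so they fall outside the statement in section 10.1 and outside this change.

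The cost is one wording amendment, a check of two forms, and possibly a rare extra screen failure. The sample size and analysis stay as they are.

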11.5 Potential Benefits to Subjects

There may be a direct benefit to participants in terms of decreased use of conventional cigarettes that are known to be more harmful than ECIGs.

11.6 Potential Benefits to Others

The potential benefit to others is that this research can provide the scientific information needed to regulate tobacco products.

12 Sharing Results with Subjects

This study is not designed to diagnose any disease or condition. However, if during the course of conducting clinical procedures, a participant is found to have a result outside of clinical norms, the participant will be contacted by the researcher either during a visit or over the phone to direct them to contact a medical provider for further evaluation. If a woman tests positive for pregnancy, the results will be shared with the participant, they will be withdrawn from the study, and they will be advised to follow up with their doctor for prenatal medical care.

13 Subject Payment and/or Travel Reimbursements

Participants will be compensated \$40 for completing visit questionnaires and procedures, and \$20 for completing the MRI scan. In addition, participants will receive a bonus of \$20 for returning all e-cig supplies at Visit 4. The total possible compensation for completing all study procedures and returning study supplies is \$220. Participants will be compensated via gift cards.

14 Economic Burden to Subjects

14.5 Costs

Participants will be provided with the study ECIG at no cost. Participants and/or insurance companies will not be responsible for costs related to study procedures and tests.

14.6 Compensation for research-related injury

It is the policy of the institution to provide neither financial compensation nor free medical treatment for research-related injury. In the event of injury resulting from this research, medical treatment is

available but will be provided at the usual charge. Costs for the treatment of research-related injuries will be charged to subjects or their insurance carriers.

15 Resources Available

15.5 Facilities and locations

The CNMRR building will be utilized for all in person participant visits. Penn State Health Zoom will be used for all remote visits.

15.6 Feasibility of recruiting the required number of subjects

In 2017, 18.7% of Pennsylvanian adults reported current cigarette smoking. With such a large proportion of smokers in the state, randomizing a total of 56 participants should be easily obtained.

15.7 PI Time devoted to conducting the research

[name] will provide scientific leadership for the project including overall study administration, design, conduct, and publication and will be responsible for all communications with the Penn State IRB. She will train and supervise the PSU research staff and will ensure that study procedures are followed.

15.8 Availability of medical or psychological resources

All of our participants will be seen by appropriately trained research staff. Any serious AEs or concerning test results will be passed on to participants along with a letter to their doctor. Any urgent health problem will require accompanying the participant to the ER, which is located on the same campus as The Center for NMR Research.

15.9 Process for informing Study Team

Weekly team meetings to discuss study procedures, questions, and issues will be conducted with all members of the PSU research team. Prior to the study start, all team members will be trained on the protocol and standard operating procedures. In addition weekly meetings will be held to discuss study progress. Current study documents including the protocol, consent, and study measures are maintained on a shared drive to ensure that all study team members have access to the most current version of all study documents. Any modifications to the study and IRB-approvals are communicated via email or via the document sharing service.

16 Other Approvals

16.5 Other Approvals from External Entities

N/A

16.6 Internal PSU Committee Approvals

Check all that apply:

- Anatomic Pathology – **Penn State Health only** – Research involves the collection of tissues or use of pathologic specimens. Upload a copy of “HRP-902 - Human Tissue For Research Form” in CATS IRB.
- Animal Care and Use – **All campuses** – Human research involves animals and humans or the use of human tissues in animals
- Biosafety – **All campuses** – Research involves biohazardous materials (human biological specimens in a PSU research lab, biological toxins, carcinogens, infectious agents, recombinant viruses or DNA or gene therapy).

- Clinical Laboratories – **Penn State Health only** – Collection, processing and/or storage of extra tubes of body fluid specimens for research purposes by the Clinical Laboratories; and/or use of body fluids that had been collected for clinical purposes but are no longer needed for clinical use. Upload a copy of “HRP-901 - Human Body Fluids for Research Form” in CATS IRB.
- Clinical Research Center (CRC) Advisory Committee – **All campuses** – Research involves the use of CRC services in any way.
- Conflict of Interest Review – **All campuses** – Research has one or more of study team members indicated as having a financial interest.
- Radiation Safety – **Penn State Health only** – Research involves research-related radiation procedures. All research involving radiation procedures (standard of care and/or research-related) must upload a copy of “HRP-903 - Radiation Review Form” in CATS IRB.
- IND/IDE Audit – **All campuses** – Research in which the PSU researcher holds the IND or IDE or intends to hold the IND or IDE.
- Scientific Review – **Penn State Health only** – All investigator-written research studies requiring review by the convened IRB must provide documentation of scientific review with the IRB submission. The scientific review requirement may be fulfilled by one of the following: (1) external peer-review process; (2) department/institute scientific review committee; or (3) scientific review by the Clinical Research Center Advisory committee. NOTE: Review by the Penn State Health Cancer Institute (PSCI) Protocol Review Committee or the PSCI Disease Team is required if the study involves cancer prevention studies or cancer patients, records and/or tissues. For more information about this requirement see the IRB website.

17 Multi-Site Study

